6.3 Monitoring during extended access

Patients fulfilling response criteria (per section 8.2) at the 16 or 20 week visit will be offered participation in the extended access cohort, and after signing consent will be permitted to continue on eltrombopag. Subjects taking eltrombopag must be evaluated at the Clinical Center every 6 months (+/- 30 days) while they remain on extended access and continue periodic laboratory monitoring in their home physician's office or the NIH every 2 weeks (+/- 7 days). Follow-up on this schedule will continue as long as they remain on eltrombopag on this clinical protocol.

Testing during NIH visit (every 6 months +/- 30 days) required for patients while on extended access and still being treated with eltrombopag:

- Acute care (Na, K, Cl, CO₂, Creatinine, Glucose, and Urea Nitrogen), Mineral (Phosphorus, Magnesium, Albumin, and Calcium), Hepatic (Alk Phosphatase, ALT, AST, Total Bilirubin, and Direct Bilirubin), and Other (Total Protein, CK, Uric Acid, and LDH) panel
- Bone marrow aspiration and core biopsy, to be stained for standard morphologic analysis and quantitation of cellularity with hematoxylin and eosin, and special stains to assess reticulin and collagen, primitive stem and progenitor cells via CD34 immunohistochemistry, and other lineage-specific or special stains as indicated to classify any abnormalities
- Bone marrow chromosomal analysis via standard cytogenetic techniques

- Flow cytometry of the peripheral blood to quantitate GPI-negative cells
- FACT questionnaire
- Iron panel (ferritin, transferrin, % saturation) at PI's discretion if indicated for iron metabolism and excretion studies
- 24 hour urine collection to determine the total iron content at PI's discretion if indicated for iron metabolism and excretion studies

On Study Monitoring every two weeks while on drug (+/- 7 days)

- Subjects may be followed by their home physician or at the Clinical Center. Progress notes and lab tests not done at the NIH will be faxed to the Research Nurse. The PI will review outside test results and these will be uploaded into CRIS and filed in the research charts, and all lab data will be recorded
- Complete blood counts with differential (every 2 weeks +/-7 days), Reticulocyte count
- ALT, AST, Total Bilirubin or Direct Bilirubin, (every two weeks +/- 7 days)

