2.4.4 Nonclinical toxicology

There were no clinically-relevant findings in toxicity studies examining the potential effects of eltrombopag on the cardiovascular, respiratory and central nervous systems. *In vitro*, eltrombopag was shown to inhibit hERG (*human Ether-à-go-go Related Gene*), the alpha subunit of a voltage-gated potassium (K⁺) channel tail current. In an *in vitro* study using isolated dog Purkinje fibers, eltrombopag was not associated with action potential prolongation, but did cause decreases in the upstroke amplitude, maximum rate of depolarization and action potential durations. In a definitive clinical QTc study with a suprathreshold dose of eltrombopag, there was no effect on cardiac repolarization.

The toxicity profile of eltrombopag has been defined in a single dose study in dogs and repeat dose toxicity studies of up to 13 weeks in mice, 28 weeks in rats and 52 weeks in dogs. In addition, repeat dose toxicity was assessed in 2 year carcinogenicity studies in mice and rats. The principal nonclinical toxicology findings associated with eltrombopag treatment include:

Cataracts (mice and rats): *In vitro* phototoxicity (3T3 and CHO cells) was observed. In mice and rats, the development of cataracts was dose- and time-dependent and the rapidly developing lenses of young mice were shown to be more susceptible. Cataract development was not associated with drug accumulation in ocular tissues. No treatment-related ocular abnormalities were evident in dogs given the maximum tolerated dose of 30 mg/kg/day (418 µg.h/mL) for 52 weeks based on detailed ophthalmologic and histologic examinations. There was no evidence of acute photo-ocular toxicity in albino or pigmented rats. An apparent delay in onset and a lower incidence of cataracts in albino mice housed in subdued versus ambient light was observed suggesting that light may contribute to cataract development in young mice. However, there was no evidence of ocular phototoxicity in young albino or pigmented mice given eltrombopag and exposed to repeated doses of solar-simulated ultraviolet radiation (UVR). B6C3F1 mice (a pigmented strain) given eltrombopag with or without UVR exposure appeared to be more susceptible than albino mice to eltrombopag-induced cataractogenesis. However, given that eltrombopag has not been shown to be

selectively retained in melanin-containing tissues, this likely represents a strain difference in sensitivity to cataract induction.

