- Increases in hepatobiliary values (ALT, AST, bilirubin, alk phos) were seen in 16/164 subjects (9.7%) in the eltrombopag group (all doses), compared with 5/67 (7.5%) in the placebo group. These elevations in liver aminotransferase were generally asymptomatic and returned to baseline after discontinuation of therapy.
- One case of thromboembolism was observed (platelet count 108,000/uL) in the eltrombopag 50 mg treatment group in a subject who died from sepsis of pulmonary origin.
- Preclinical findings that indicated potential for phototoxicity, cataracts and renal tubular toxicity did not appear to translate to clinical consequences during short-term use.
- Transient decreases in platelet counts to levels below baseline were observed in both treatment groups after eltrombopag treatment ended. However, the decreases in platelet count were not accompanied by a clinically meaningful increase in bleeding symptoms.

TRA105325 (Extend) (chronic ITP Study): An open-label, dose-modification, Phase 3 extension study to evaluate the safety and efficacy of eltrombopag for the treatment of 302 subjects with ITP who were previously enrolled in an eltrombopag trial. Of the 302 subjects enrolled in the study, 186 (62%) achieved a platelet count ≥ 50 Gi/L in the absence of rescue therapy for $\geq 50\%$ of on-treatment assessments. Response rate in subjects with and without concomitant ITP medication used as baseline was 54% and 65%, respectively, and in subjects who were or were not splenectomised at baseline was 51% and 68%, respectively. The incidence of any bleeding symptoms (WHO grades 1-4) decreased from 57% at baseline to 16% at Week 52, 19% at Week 104, 12% at Week 156, and 14% at Week 208. Clinically significant bleeding (WHO grades 2-4) decreased from 17% at baseline to 4%, 5%, 0%, and 0% at Weeks 52, 104, 156, and 208, respectively.

TRA108057 (Repeat) (chronic ITP study): An ongoing, Phase II, multi-center, open label single group repeat dose study to evaluate the efficacy, safety and tolerability of repeated, short term administration of eltrombopag initially administered as 50 mg tablets once daily in subjects with previously treated chronic ITP (66 subjects with ongoing enrollment). In general, the results from the ongoing REPEAT and EXTEND studies confirmed the safety and efficacy profile noted in the completed TRA100773A and TRA100773B and are summarized below:

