In a controlled trial in patients with chronic liver disease and thrombocytopenia not related to ITP undergoing elective invasive procedures (N = 292), the risk of thrombotic events was increased in patients treated with 75 mg of PROMACTA once daily. Seven thrombotic complications (six patients) were reported in the group that received PROMACTA and three thrombotic complications were reported in the placebo group (two patients). All of the thrombotic complications reported in the group that received PROMACTA were portal vein thrombosis (PVT). Symptoms of PVT included abdominal pain, nausea, vomiting, and diarrhea. Five of the six patients in the group that received PROMACTA experienced a thrombotic complication within 30 days of completing treatment with PROMACTA and at a platelet count above 200 x 10⁹/L. The risk of portal venous thrombosis was increased in thrombocytopenic patients with chronic liver disease treated with 75 mg of PROMACTA once daily for 2 weeks in preparation for invasive procedures.

Cataracts

In the three controlled clinical trials in adults with chronic ITP, cataracts developed or worsened in 15 (7%) patients who received 50 mg of PROMACTA daily and 8 (7%) placebo-group patients. In the extension trial, cataracts developed or worsened in 11% of patients who underwent ocular examination prior to therapy with PROMACTA. In the two controlled clinical trials in patients with chronic hepatitis C and thrombocytopenia, cataracts developed or worsened in 8% of patients treated with PROMACTA and 5% of patients treated with placebo.

Cataracts were observed in toxicology studies of eltrombopag in rodents. Perform a baseline ocular examination prior to administration of PROMACTA and, during therapy with PROMACTA, regularly monitor patients for signs and symptoms of cataracts.

Clinical Experience:

For full information on clinical experience with eltrombopag in for the treatment of all approved indications, see PACKAGE INSERT.

Severe Aplastic Anemia: In the single-arm, open-label trial, 43 patients with severe aplastic anemia received PROMACTA. Eleven patients (26%) were treated for greater than 6 months and 7 patients (16%) were treated for greater than 1 year. The most common adverse reactions (greater than or equal to 20%) were nausea, fatigue, cough, diarrhea, and headache.

Adverse Reactions (≥10%) from One Open-label Trial in Adults with Severe Aplastic Anemia

Adverse Reaction	PROMACTA (n = 43) (%)
Nausea	33
Fatigue	28
Cough	23

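### No scheduled visit examines the eyes or asks about vision, so a low cataract count in the toxicity profile would be weak evidence of absence

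*Combined protocol and SAP*

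**What the plan says.** The cataract paragraph of section 10.3.1 carries this precaution: "Perform a baseline ocular examination prior to administration of PROMACTA and, during therapy with PROMACTA, regularly monitor patients for signs and symptoms of cataracts". It also gives the background rates:

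- Controlled adult ITP trials: "cataracts developed or worsened in 15 (7%) patients who received 50 mg of PROMACTA daily and 8 (7%) placebo-group patients".
- ITP extension trial: "cataracts developed or worsened in 11% of patients who underwent ocular examination prior to therapy with PROMACTA".
- Controlled hepatitis C trials: "cataracts developed or worsened in 8% of patients treated with PROMACTA and 5% of patients treated with placebo".

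Section 2.4.4 reports that in mice and rats "the development of cataracts was dose- and time-dependent". The same section says: "No treatment-related ocular abnormalities were evident in dogs given the maximum tolerated dose". Section 2.4.6 adds that the preclinical eye, skin and kidney signals "did not appear to translate to clinical consequences during short-term use".

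The schedules are in sections 6.1 to 6.4 and the two tables of Appendix B. For extended access on drug, section 6.3 states: "Subjects taking eltrombopag must be evaluated at the Clinical Center every 6 months (+/- 30 days) while they remain on extended access". Section 6.3.1 sets a 12-monthly evaluation for subjects off drug. Section 8.2 makes the CTCAE toxicity profile part of the primary endpoint. Section 9.2.2 has every adverse event recorded that the team observes or is told about.

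**The concern.** The protocol states a precaution that its own schedule does not carry out. The neighbouring hepatotoxicity precaution fares differently. The label text asks for liver tests every two weeks during dose adjustment, and section 6.2 and Appendix B schedule them at that interval. Cataract has no matching procedure, and no reason is given.

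Two things are lost:

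- **Baseline status.** Without an ocular baseline, a cataract found later cannot be reliably classed as new or pre-existing. Section 9.2.2 uses that distinction: a labelled event is exempt from reporting unless, among other conditions, it was absent at the baseline examination.
- **Frequency.** An untargeted count is likely to be too low to set beside the listed rates. The 11% extension-trial figure comes from patients examined before therapy. Section 9.2.2 also makes a frequency above the listed one a trigger for reporting.

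The stake is how the safety report is read. Nobody is scheduled to look or ask, so a zero could be taken to mean that cataract did not occur.

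**Working it through.** The plan gives no cataract figure to reproduce. The check has two parts.

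**1. The schedules, read for any ocular item**

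| Time point | Clinical item listed | Eye examination or vision question |
|---|---|---|
| Pre-study (6.1, Appendix B) | History and physical | None |
| Week 16/20 (6.2, Appendix B) | Clinical assessment and vital signs (6.2); history and physical (Appendix B) | None |
| Extended access on drug, 6-monthly (6.3, Appendix B) | No history or physical listed | None |
| Extended access off drug, 12-monthly (6.3.1, Appendix B) | No history or physical listed | None |
| Optional off-study visit (6.4) | History and physical | None |

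**2. What a low count would show**

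Inputs: 33 evaluable subjects, and up to 38 enrolled if dropouts are replaced (8.3). The wider number matters because a replaced subject who took drug still counts for toxicity. The listed rates are 7% and 11% (10.3.1).

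*Complete capture, no cases.* The one-sided 95% exact upper limit is 1 − 0.05^(1/n).

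- n = 33: 1 − 0.05^(1/33) = 0.0868, or 8.7%.
- n = 38: 1 − 0.05^(1/38) = 0.0758, or 7.6%.

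The extended-access group is smaller. At the design response rates of 20% and 40%, it would be 33 × 0.20 = 6.6 and 33 × 0.40 = 13.2, about 7 and 13 subjects. The upper limits for zero cases are then 34.8% and 20.6%. The alternative is 40% or more, so 13 is not a ceiling.

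*Incomplete capture.* Let s be the share of cataracts that general recording picks up. The documents give no value, so s is an assumption, shown over a range. The chance of recording none when the true rate is p is (1 − p·s)^n.

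| s (assumed) | p = 7%, n = 33 | p = 11%, n = 33 | p = 7%, n = 38 | p = 11%, n = 38 |
|---|---|---|---|---|
| 1 | 9.1% | 2.1% | 6.3% | 1.2% |
| 0.5 | 30.9% | 15.5% | 25.8% | 11.7% |
| 0.25 | 55.8% | 39.8% | 51.1% | 34.7% |
| 0.10 | 79.3% | 69.4% | 76.6% | 65.7% |

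For 0 of 33, dividing the 8.68% limit by s gives a limit on the true rate of about 17% at s = 0.5 and 35% at s = 0.25.

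*Size of any drug effect in the listed data.* The excess over placebo is 7% − 7% = 0 points in ITP and 8% − 5% = 3 points in hepatitis C. In 33 subjects that is 0 to 33 × 0.03 = 0.99 cases; in 38 it is 0 to 38 × 0.03 = 1.14.

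**The case against.** The strongest reply is that nothing turns on this. No section plans a cataract rate, a comparison of such a rate or a claim of ocular safety, and cataract is not named in 8.2 or 8.5. The trial has one arm, and the ITP rate equalled placebo, so even a perfect count could not attribute cataract to the drug. The dog data were negative, as was the definitive juvenile rat study (2.4.4), and short-term clinical use raised no signal. A symptom question neither restores a baseline nor finds asymptomatic cataract. All of that stands, and it keeps the point small. It does not explain why a stated precaution has no counterpart in the schedule, or make an unqualified zero informative.

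Several stronger readings are tempting, and the documents do not support them:

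- *Cataract is not captured at all.* Observed and reported events are recorded (9.2.2), progress notes from home physicians go to the research nurse, and subjects are still evaluated every 6 or 12 months. The IRB receives adverse events at continuing review, with limited exclusions (9.2.4).
- *The protocol breaches a procedure of its own.* The precaution is reproduced prescribing text within a risk section, not a study procedure. Its absence from the schedule also does not show that clinicians ignore it.
- *Subjects face six times the exposure behind the 7% rate.* The ratio 300/50 compares maximum nominal doses, and only for non-East-Asian adults. The maximum is 150 mg for East Asian adults, children have fixed doses of 150 mg or less at ages 6 to 18 and weight-based doses below that, and extended access uses the lowest dose that holds counts (3.0) or stops the drug after a robust response (5.5).
- *A rate with an exact interval among subjects who had an eye examination before treatment would settle it.* No on-treatment examination exists, so the numerator would still be under-counted. The subgroup would also be self-selected and of unknown size.

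**Conclusion.** The gap is real and minor. Following the schedule as written does not carry out the precaution in 10.3.1, and cataract reaches the toxicity profile only through untargeted recording. A low or zero count is therefore weak evidence of absence. Complete capture would leave an upper limit of 8.7% to 7.6% for zero of 33 to 38 subjects. Incomplete capture widens it by an amount that the documents do not allow one to estimate.

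This rests on the schedules in section 6 and Appendix B being the full set of planned assessments. The consent pages are not available, so any instruction to patients to report changes in vision could not be checked. That a low count would be misread is an inference, not something that the plan states. The efficacy test and the stopping rule are unaffected. The case for acting is that the change costs almost nothing.

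**What to change.** - Add *interval history including new visual symptoms* to the week 16/20 visit (6.2), the six-monthly on-drug visit (6.3), the 12-monthly off-drug visit (6.3.1) and the matching columns of Appendix B.
- Ask each subject once whether the eyes were examined before the first dose, and file any record.
- Code each cataract as new, worsened or baseline unknown.
- Report cataract as counts only, and state in the safety report that it was not systematically assessed by examination.

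The cost is one question at visits that already occur, one request for records, one coding field and one sentence. No examiner, procedure or additional subject is needed. The limits should be accepted openly: asymptomatic cataract will still be missed, a missing ocular baseline is not restored, and the question reaches only subjects still in follow-up, whose number is not given. The reporting sentence is useful however many remain.

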3.0 STUDY DESIGN

[figure not shown]
The study is designed as a non-randomized, Phase II, dose modification study of the oral TPO-R agonist eltrombopag in moderate aplastic anemia patients or those with bone marrow failure with unilineage cytopenia. The primary endpoint is measured at 16 to 20 weeks (+/- 7 days). Subjects with evidence for a clinical response in any lineage at 16 weeks but not yet meeting full primary endpoint response criteria, and who are tolerating investigational treatment, may receive an additional 4 weeks of eltrombopag and be reassessed after 20 weeks (+/- 7 days). At that time, if they meet primary endpoint response criteria, they will be eligible to enter the extended access part of the study. If they do not meet primary endpoint response criteria, eltrombopag will be discontinued. Subjects who cannot tolerate the medication or fail to respond by 16 to 20 weeks (+/- 7 days) will go off study. Drug dose during extended access will be at the lowest dosage that maintains stable blood counts or taken off drug for robust response until they meet off study

criteria or the study is closed. If subjects are taken off drug for robust response during extended access and maintain response, they will be taken off study after 3years.

Protocol Schema prior to January 8, 2015:

Protocol Schema after January 8, 2015:

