5.5 Extended access to study drug

Subjects with improvement in blood counts or transfusion requirements but not yet meeting response criteria at 16 weeks may continue study medication for an additional 4 weeks (to ensure eligibility) prior to being consented for entry into the extended access part of the trial. Subjects that have their response assessment extended an additional 4 weeks and have a response will be able to go on the extended access part of the trial after signing the consent. Per dosing criteria given in section 5.2, patients may remain on the extended access as long as they maintain a treatment response.

Dose adjustments during extended access: Eltrombopag will be discontinued in patients that reach robust hematologic response (platelets >50,000/ μ L and Hb > 10 g/dL in the absence of transfusions, and neutrophils > 1,000) for more than 8 weeks. In patients who maintain initial response criteria (but do not meet robust response criteria in all three lineages) and show no further clinically-significant improvement in their counts over a 6 month period eltrombopag can be stopped at PI's discretion. Eltrombopag can be re-initiated at PI's discretion if peripheral cell counts drop below numbers measured when the patient entered the study or if platelets drop to <30,000/ μ L, Hb to <9g/dL, or ANC to <500/ μ L. Once count stabilization again occurs, a slow dose reduction by 50 mg increments can be performed to identify the lowest dose necessary to keep counts over these thresholds.

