6.3.1 Subjects that have drug stopped for robust response

Subjects that have drug stopped for robust response or for a stable response with no significant improvement in their counts over a 6 month period will have blood counts monitored every three months be seen for up 3 years after the last dose of drug, and then be taken off study as long as the subject maintains response. Subjects off drug must be evaluated at the NIH Clinical Center every 12 months (+/- 30 days). Evaluations designated by the “***” below will only need to be completed for subjects at response assessment every 6 months. Subjects may be seen for monthly interim visits at the NIH or at their referring home health care provider. At the clinical investigator's discretion, participants may be evaluated more frequently if medically indicated based on disease status. If subjects are to be followed at home, progress notes (if available) and laboratory results from the home health care provider and laboratory must be faxed to the study research nurse.

Testing during NIH visit (every 12 months) required for patients while on extended access but off eltrombopag:

- Complete blood counts with differential (monthly +/- 7 days for 6 months off eltrombopag, then every 3 months for 3 years)
- Bone marrow aspiration and core biopsy, to be stained for standard morphologic analysis and quantitation of cellularity with hematoxylin and eosin, and special stains to assess reticulin and collagen, primitive stem and progenitor cells via CD34 immunohistochemistry, and other lineage-specific or special stains as indicated to classify any abnormalities. (every 12 months +/- 60 days for three years)
- Bone marrow chromosomal analysis via standard cytogenetic techniques (every 12 months +/- 60 days for three years)
- Flow cytometry of the peripheral blood to quantitate GPI-negative cells (every 12 months +/- 60 days for three years)
- FACT questionnaire (every 12 months +/- 60 days for three years)
- Iron panel (ferritin, transferrin, % saturation) at PI's discretion if indicated for iron metabolism and excretion studies (every 12 months +/- 60 days)
- Lymphocyte phenotyping (TBNK flow cytometry)
- Research blood as detailed in section 7
- 24 hour urine collection to determine the total iron content at PI's discretion if indicated for iron metabolism and excretion studies (every 12 months +/- 60 days)

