FACT Questionnaire		X (‡)								X**		X
PK(&)										X**		

* stained for standard morphologic analysis and quantitation of cellularity with hematoxylin and eosin, and special stains to assess reticulin and collagen, primitive stem and progenitor cells via CD34 immunohistochemistry, and other lineage-specific or special stains as indicated to classify any abnormalities

(\$) Within 7 days of consent

(†) Within 12 weeks prior to consent

(‡) Only adults subjects 18 years and older who read English or Spanish will complete the survey

** Evaluations will only need to be completed for subjects at response assessment either at week 16 or 20.

(&) at PI's discretion

Schedule of events Extended Access phase

Visit/ Time Point	Extended Access - On eltrombopag		Extended Access - Off eltrombopag		
	Every 2 Weeks (+/- 7 days)	Every 6 Months (+/- 30 days)	monthly +/- 7 days for 6 months off eltrombopag, then every 3 months for 3 years	Every 12 months for 3 years (+/- 60 days)	Off study (optional) (+/- 30 days)
Procedure					
Complete blood count with differential	X	X	X	X	X
Reticulocyte count					X
Hepatic (Alk Phosphatase, ALT, AST, Total Bilirubin, and Direct Bilirubin)	X	X			X
Acute care (Na, K, Cl, CO2, Creatinine, Glucose, and Urea Nitrogen)		X			
Mineral (Phosphorus, Magnesium, Albumin, and Calcium)		X			
Total Protein, CK, Uric Acid, and LDH		X			
Research Blood				X	X
Bone marrow aspiration and core biopsy, stained for standard morphologic analysis and quantitation of cellularity with hematoxylin and eosin, and special stains to assess reticulin and collagen, primitive stem and progenitor cells via CD34 immunohistochemistry, and other lineage-specific or special stains as indicated to classify any abnormalities		X		X	X
Bone marrow chromosomal analysis via standard cytogenetic techniques		X		X	X
Flow cytometry of the peripheral blood to quantitate GPI-negative cells		X		X	X
Lymphocyte peripheral blood phenotyping (analysis of T, B, and NK subsets via flow cytometry)				X	X
Iron panel (ferritin, transferrin, % saturation) (&)		X		X	
24 hour urine collection to determine the total iron content (&)		X		X	
FACT questionnaire (‡)		X		X	

(%) only every 12 months +/- 60 days for robust responders that discontinue eltrombopag

(‡‡)not required for robust responders

(&) at PI's discretion

(‡) Only adults subjects 18 years and older who read English or Spanish will complete the survey

11-H-0134

[name].

01/02/2019 (Amendment HH)

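### No pregnancy test is scheduled in extended access or before eltrombopag is restarted, although section 8.6.2 makes pregnancy a reason to stop drug there

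*Combined protocol and SAP*

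**What the plan says.** **Initial phase.** Section 6.1 requires a pregnancy test within 7 days of first dose. Appendix B shows tests at weeks 4, 8, 12 and 16/20, and 6.2 names the week 16 and week 20 tests. Section 6.2 also allows the referring provider to run them.

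**Extended access, on drug.** Section 6.3 sets out the 6-monthly NIH-visit tests "required for patients while on extended access and still being treated with eltrombopag" and a separate 2-weekly list of blood counts, reticulocytes and liver tests. Neither contains a pregnancy test.

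**Extended access, off drug.** The 6.3.1 list, "required for patients while on extended access but off eltrombopag", has none either. Blood counts in that phase are taken "monthly +/- 7 days for 6 months off eltrombopag, then every 3 months for 3 years".

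**Appendix B.** The extended-access table, including the columns headed "Extended Access - On eltrombopag", has no pregnancy-test row.

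**Duration and restart.** Under 5.5, "patients may remain on the extended access as long as they maintain a treatment response". There are limits. In 5.5, "Eltrombopag will be discontinued in patients that reach robust hematologic response" lasting more than 8 weeks, and the PI may stop drug after 6 months without further improvement. In 3.0, "Drug dose during extended access will be at the lowest dosage that maintains stable blood counts". On restarting, 5.5 says "Eltrombopag can be re-initiated at PI's discretion if peripheral cell counts drop below numbers measured when the patient entered the study", or if counts fall below stated thresholds. It attaches no pregnancy test.

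**Action on pregnancy.** Section 8.6.2 includes pregnancy among the reasons to discontinue eltrombopag, both in the first 16 weeks and in the extension. Section 9.3 calls for immediate discontinuation.

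**The concern.** The plan requires an action in the extension (stop drug if pregnant) but no longer collects the information that would trigger it. What remains is contraception for the duration of participation and the woman's own report of a known or suspected pregnancy (4.2.9, 10.1, 10.3.2). Those safeguards apply equally in the initial phase, where the protocol still tests about every 4 weeks. No reason is given for ending the tests while exposure continues without a calendar limit.

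The restart is the weaker spot. A woman may be off drug for up to 3 years, untested throughout, and then resume treatment on blood counts and PI discretion alone. What is at stake is avoidable fetal exposure in a small number of women; no trial result depends on it.

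**Working it through.** The plan states no figure to reproduce. The check is a count of scheduled tests, followed by a rough scale.

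**1. Scheduled pregnancy-test time points**

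| Period | Source | Tests |
|---|---|---|
| Pre-study | 6.1, Appendix B | 1 |
| Weeks 4, 8, 12, 16/20 | 6.2, Appendix B | 4 |
| Extended access, on drug | 6.3, Appendix B | 0 |
| Extended access, off drug | 6.3.1, Appendix B | 0 |
| Before a restart | 5.5 | 0 |

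Text and table agree on the zeros, so a misread table does not explain them. The 6.3 list is not exhaustive, since 7.2 adds serum thrombopoietin at the 6-monthly visits. The other sections that mention pregnancy or its testing (6.4, 8.6.2, 9.3, 10.1, 10.3.2, 10.5) supply no test in extended access.

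**2. Rates**

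- Initial phase, on drug: 4 tests in 16 weeks, or one per 4 weeks.
- Extended access, on drug: 52 / 2 = 26 draws and 2 NIH visits a year, with 0 pregnancy tests.
- At the initial-phase interval: 52 / 4 = 13 tests per woman-year.

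**3. Number of women, for scale only**

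The documents do not state how many women of childbearing potential there are.

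- Section 8.3 accepts the null hypothesis at 10 or fewer responders, so 11 is the smallest count that rejects it.
- Section 10.1 expects 40% females among aplastic anemia patients evaluated at the institution.
- Assuming that share holds among responders and that all of them enter extended access: 11 x 0.40 = 4.4 women, before restricting to childbearing potential.
- At that count the added testing is at most 4.4 x 13 = 57 tests a year.

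More responders would raise these figures; the restriction to childbearing potential would lower them.

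**The case against.** The case for leaving the schedule alone has several parts.

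- **No rule is broken.** Section 8.6.2 says what to do if an event occurs. It also lists events such as stroke and hypersensitivity that have no scheduled screen. This is right: the point is a design choice, not a contradiction. Pregnancy differs in that a simple test exists and the protocol itself uses it in the initial phase.
- **Other safeguards exist.** Contraception is required throughout, unwillingness to use it is itself a reason to stop, the week 16/20 test covers entry to extended access, and entry needs a newly signed consent. These reduce the gap but do not detect a later pregnancy. The discretion in 6.3.1 to evaluate more often is tied to disease status and mandates no pregnancy test.
- **The risk is limited.** Section 2.4.4 reports no teratogenicity in rats or rabbits, with embryolethality at a maternally toxic dose in rats. That stands, but 10.3.2 says human fetal effects and teratogenicity are unknown. The rat dose with implantation loss is put in 10.3.1 at 6 times ITP exposure at 75 mg/day and 3 times hepatitis C exposure at 100 mg/day. The trial allows 300 mg/day. If exposure is proportional to dose (an assumption), the multiples become 6 x 75/300 = 1.5 and 3 x 100/300 = 1. Most extension patients should be on less, because 3.0 calls for the lowest effective dose.
- **The 4-week interval is not dictated.** The labelling text in 10.3.1 sets none. In addition, weeks 4, 8 and 12 appear only in Appendix B, and its footnote requires the last test at week 16 or week 20, so a gap of 8 weeks after week 12 is possible. A test at each 6-monthly visit plus one before a restart would be a weaker alternative.
- **The reach may be small.** The 2019 amendment describes some enrollment in the past tense, so the change may affect only women still in extended access.

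**Conclusion.** The point holds, as a minor one. Scheduled pregnancy testing falls from about one test every 4 weeks to none, although drug continues and 8.6.2 still makes pregnancy a reason to stop it. A restart after as much as 3 years off drug needs no test either. The likely number of women is small: about 4 at the smallest successful responder count, before the restriction to childbearing potential and under the assumptions above. The sample size, the error rates and the primary analysis are unaffected. One limit applies: the consent pages and a small part of the protocol text were not available for this check, so a test mentioned only there cannot be excluded. Even then, it belongs in the monitoring sections and in Appendix B.

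**What to change.** 1. **Section 6.3 and Appendix B.** Add an HCG test for women of childbearing potential to the on-drug laboratory list, every 4 weeks at every second existing 2-weekly draw. Add the matching row to the on-drug columns of the extended-access table.
2. **Section 5.5.** Require a negative test within 7 days before any re-initiation. This is the window 6.1 uses before first dose. Appendix B gives the baseline window relative to consent instead, so the amendment should tie the restart test to the dose.

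The cost is an amendment to two sections and one table row, then about 13 inexpensive tests per woman-year at draws already taken, and one test per restart. No new visit or invasive procedure is needed, and providers near home already run the test in the initial phase. The one real drawback is that a restart could wait for a result. If 4-weekly testing is judged too frequent, a test at each 6-monthly visit plus the pre-restart test is the least that would close the gap, but a pregnancy could then go untested for about 6 months on drug.
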